Figure 2: Dentapen used in the study.

Injection with Vibraject

After drying the mucosa, a cotton-tipped applicator with a 20% benzocaine gel (Topox; Sultan Healthcare, Inc., York, PA) was placed for 60 seconds using a digital timer. After 60 seconds, the target site was wiped with another 2-inch by 2-inch cotton gauze and injecting 0.5 cartridge (0.9 mL) of 3% mepivacaine hydrochloride with no epinephrine (Henry Schein, Melville, NY) which was stored in room temperature. The needle was advanced into the tissue until it was estimated to be over the root apex while remaining parallel to the tooth's long axis. The Vibraject was activated after aspiration to deposit the solution slowly at approximately 50 seconds (time necessary to infiltrate 0.5 mL of anesthetic with the dentapen system) for both groups. The time factor was therefore limited to prevent a possible confounding effect in the patients' pain perception. Following cartridge deposition, the operator adjusted the participant to an upright

seated position so that he or she could independently record his or her perceived pain on the Visual Analogue Scale. The Vibraject was selected as the vibrator due to its simple design, battery operation, and ability to be easily attached to a syringe with minimal adjustment to conventional injection procedures. Also, compared to other vibration gadgets, it is reasonably affordable.

Figure 3: Vibraject used in the study.

Visual Analogue Scale scale

The Visual Analogue Scale score was stratified into distinct categories: "0" denoted absence of pain, scores ranging from "1-3" indicated mild pain, "4-6" signified moderate pain, "7-9" represented severe pain, and the maximum score of "10" was designated as indicative of the utmost intensity of pain conceivable.

Statistical Analysis

The statistical analysis for this study was conducted using SPSS Version 20 (IBM-SPSS Inc., Chicago, IL), a robust statistical software package that allows for detailed data management and analysis. The primary statistical tests employed were the paired T-test for analysing the heart rate data and the Wilcoxon test for the Visual Analogue Scale pain scores.

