The paired T-test was chosen for the heart rate data as it is designed to compare the means of two related groups, such as the same patients' heart rates before and after each injection. This test is particularly suitable for assessing whether there is a statistically significant change in heart rate following the administration of local anaesthesia.

For the Visual Analogue Scale pain scores, the Wilcoxon test was utilized. This non-parametric test is ideal for data that are not normally distributed and is used for comparing two related samples, matched samples, or repeated measurements on a single sample. In this study, it was employed to evaluate the differences in pain scores between the two different injection techniques on the same patients.

A p-value of 0.05 or less was considered statistically significant. This conventional threshold indicates that there is only a 5% likelihood that the observed differences occurred by chance. Thus, if the p-value is less than or equal to 0.05, the results are deemed statistically significant, suggesting a real difference between the two techniques that is not due to random variation.

RESULTS

Table 1 shows the demographic characteristics of the study population, offering insights into both age and gender distribution. The mean and standard deviation for age provides a central tendency and variability measure, while the gender distribution details the proportion of males and females in the sample. The mean age of the patients was 36.1 (SD 9.33) years, with the majority being males (87.5%).

Table 1: Descriptive statistics of study participants (N=40), highlighting age and gender distribution

Study variables	N (%)
Age in years (mean \pm SD)	36.1 \pm 9.33
Gender	
• Male	35 (87.5%)
• Female	05 (12.5%)

Figure 4 presents the study population's preferred method for injecting anaesthesia. The highest number of the participants showed interest in the Dentapen® method (n = 25, 62.5%) while 15 participants showed inclination towards the Vibraject method (37.5%).

[figure not shown]

Figure 4: Preferred method of injecting local anaesthesia by the study population

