Table 2 demonstrates descriptive statistics related to heart rate measurements, including mean, standard deviation, and standard error of the mean for different conditions. The mean heart rate before treatment is slightly lower for Dentapen® (70.225) compared to Vibraject (70.775). The mean heart rate after treatment is higher for Dentapen® (71.75) compared to Vibraject (71.05). Both Dentapen® and Vibraject showed an increase in mean heart rate after treatment.

Table 2: Heart rate before and after the procedure

		Mean	N	Std. Deviation	Std. Error Mean
Overall	Heart rate before	70.5000	80	10.16572	1.13656
	Heart rate after	71.4000	80	9.59905	1.07321
Dentapen®	Heart rate before	70.2250	40	10.04984	1.58902
	Heart rate after	71.7500	40	9.94794	1.57291
Vibraject	Heart rate before	70.7750	40	10.40091	1.64453
	Heart rate after	71.0500	40	9.35058	1.47846

Table 3 indicates a statistically significant increase in mean heart rate measurements following Dentapen® injection ($p=0.010$). However, no significant differences were observed in the mean heart rate measurements between the overall and Vibraject before and after injection ($p>0.05$).

Table 3: Comparison of mean heart rate measurements before and after injections with Dentapen® and Vibraject

	Paired Differences					t	P-value §
	Mean	Std. Deviation	Std. Error	95% Confidence Interval of the Difference			

						Lower	Upper		
Overall	Heart rate before - Heart rate after	- .90000	4.18133	.46749	-1.83051	.03051	- 1.925	0.058	
Dentapen®	Heart rate before - Heart rate after	- 1.5250	3.56613	.56386	-2.66550	-.38450	- 2.705	0.010 **	
Vibraject	Heart rate before - Heart rate after	- .27500	4.67940	.73988	-1.77155	1.22155	-.372	0.712	

§ P-value has been calculated using paired sample t-test.

** Significant at p<0.05 level.

Table 4 depicts the mean Visual Analogue Scale score. The mean score of Vibraject (2.175) was observed higher than that of Dentapen (1.550). However, the results yielded an insignificant difference (p=0.105). The overall mean Visual Analogue Scale score was 1.863.

Table 4: Comparison of Visual Analogue Scale between Dentapen® and Vibraject

	Mean	N	Std. Deviation	Std. Error Mean	P-value §
Overall	1.863	80	1.605	0.179	
Dentapen®	1.550	40	1.467	0.232	0.105
Vibraject	2.175	40	1.693	0.268	

§ P-value has been calculated using Mann Whitney Z-test.

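### The 0.05 rule reads any significant test as a difference between the devices, but no outcome is ranked, no multiplicity rule is given, and the heart-rate tests do not compare devices

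*Combined protocol and SAP*

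**What the plan says.** The combined document lists three outcomes under Outcome Measurement (pain on the Visual Analogue Scale, heart rate before and after each injection, and patient preference) and does not rank them. The Sample Size section does not say which outcome the 40 patients were sized for.

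Under Statistical Analysis, the word primary is attached to tests: "The primary statistical tests employed were the paired T-test for analysing the heart rate data and the Wilcoxon test for the Visual Analogue Scale". The two tests ask different questions. The paired t-test is for related measurements, "such as the same patients' heart rates before and after each injection". For the Wilcoxon test the document says that "it was employed to evaluate the differences in pain scores between the two different injection techniques on the same patients".

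One rule then covers everything. "A p-value of 0.05 or less was considered statistically significant". The threshold is explained as meaning that "there is only a 5% likelihood that the observed differences occurred by chance", and a result that meets it is read as "suggesting a real difference between the two techniques that is not due to random variation". No hierarchy, split of alpha or adjustment is described.

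The Results give four p-values. Table 3 has three before-after heart-rate tests: overall 0.058, Dentapen 0.010, Vibraject 0.712. Table 4 has one pain comparison of the devices: 0.105, with a footnote naming the Mann-Whitney test. Preference (25 for Dentapen, 15 for Vibraject) is reported without a test.

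**The concern.** The rule draws one conclusion, that the techniques differ, from any test that reaches 0.05. Two things go wrong.

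First, several tests are read at 0.05 with none named as decisive, so the chance that at least one of them is falsely significant exceeds 5%.

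Second, a before-after test within one device has the null hypothesis that heart rate does not change after that injection. Rejecting it says nothing about the other device. Finding significance with one device and not with the other is not a test of the difference between them.

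The point matters here because the only p-value below 0.05 is the Dentapen before-after one. The results also do not all point the same way: mean pain and preference favour Dentapen, while heart rate rises more after Dentapen. With no deciding outcome, the message depends on which result a reader picks.

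**Working it through.** **1. Reproducing Table 3.** Inputs are the means, SDs and n in Table 3. With t = mean / (SD/√n), two-sided:

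- Overall: 0.900 / (4.18133/√80) = 1.925, p = 0.0578 (stated 0.058).
- Dentapen: 1.525 / (3.56613/√40) = 2.705, p = 0.0101 (stated 0.010).
- Vibraject: 0.275 / (4.67940/√40) = 0.372, p = 0.7121 (stated 0.712).

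The table is internally correct, and its tests are two-sided before-after tests.

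**2. Familywise false-positive rate.** For k independent tests at 0.05, with every null true, the rate is 1 − 0.95^k:

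- k = 1: 5.0%
- k = 2: 9.75%
- k = 4: 18.5%

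The four reported tests are not independent, because the overall row pools the two device rows. A simulation of the four tests (100,000 trials per setting, n = 40, Table 3 SDs, all nulls true) gave 15.9% with uncorrelated changes, and 16.5% to 18.0% for assumed within-patient correlations of 0.3 to 0.7. Part of that rise comes from treating 80 injections in 40 patients as independent, which lifts the overall test's own error to about 8% to 13%. Two tests with correlation 0 to 0.8 give 9.75% down to 7.8%.

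**3. Effect of a simple adjustment.** Bonferroni over four: Dentapen heart rate 0.0101 × 4 = 0.040, still below 0.05. Pain at 0.105 is above 0.05 with or without adjustment. No reported label changes.

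**4. What each test can show.** Three of the four p-values concern change after injection. Only the pain test compares the devices. The weakness of reading a before-after p-value as a device difference can be illustrated. Suppose, as an assumption, that both devices truly raise heart rate by the pooled 0.9, so that they do not differ. The Dentapen test has standard error 0.56386, so its expected t is about 0.9/0.56386 = 1.60. It is then significant with probability of about 1 − Φ(1.96 − 1.60) = 0.36 (0.34 by the noncentral t). Under the rule, each such result would be read as a device difference.

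**5. The comparison that is missing.** The difference in mean change is 1.525 − 0.275 = 1.25. Its SD depends on the within-patient correlation r of the two changes, which the document does not give:

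SD = √(3.56613² + 4.67940² − 2r × 3.56613 × 4.67940), SE = SD/√40, 39 degrees of freedom, critical value 2.023.

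| Assumed r | SD | SE | t | p | 95% CI |
|---|---|---|---|---|---|
| 0 | 5.88 | 0.930 | 1.34 | 0.19 | −0.63 to 3.13 |
| 0.5 | 4.23 | 0.669 | 1.87 | 0.07 | −0.10 to 2.60 |
| 0.7 | 3.35 | 0.530 | 2.36 | 0.02 | 0.18 to 2.32 |

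**6. How firm the pain result is.** The 0.105 comes from a test for independent samples. As a rough guide only, a paired t on the Table 4 figures (difference 2.175 − 1.550 = 0.625, SDs 1.693 and 1.467, n = 40) gives p of about 0.085, 0.042 or 0.017 at assumed correlations of 0, 0.3 or 0.5. The planned signed-rank result cannot be derived from the tables.

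**The case against.** The case on the other side is substantial.

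- A reader might infer that heart rate and pain are declared co-primary outcomes. The text calls the tests primary, not the outcomes. Co-primary is a fair inference, since nothing else separates them, but the document does not say so. The overall heart-rate row also appears only in the Results and is not in the described method.
- A reader might infer that the true chance-finding rate is 10% to 19% in place of the stated 5%. That sets a familywise rate against a per-test threshold, and the range assumes independence and that every null is true. The 5% sentence is wrong for another reason: alpha is not the probability that an observed difference arose by chance. It would be wrong with a single test.
- A reader might infer that 10% to 19% is the risk of wrongly preferring one device. It is not. Only the pain test compares devices, so the nominal error of a between-device claim, as analysed, is 5%.
- Adjustment changes no reported label. The Results text is also restrained: "Table 3 indicates a statistically significant increase in mean heart rate measurements following Dentapen® injection", while "no significant differences were observed in the mean heart rate measurements between the overall and Vibraject before and after injection", and the pain difference is called insignificant. Nowhere do the supplied Results claim a device difference from heart rate.

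All of this stands, and it limits the point. It does not remove it. The written rule makes no distinction between the before-after tests and the pain test, and the between-device heart-rate comparison is absent.

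**Conclusion.** The point holds in a limited form. No outcome is ranked, no multiplicity rule is given, and the decision rule attaches a between-device conclusion to tests that are mostly not between-device. The familywise rate is up to about 10% for two tests and 19% for four under independence, and about 16% to 18% for the four with shared data and the assumed correlations.

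The more serious part is the misreading that the rule permits. The Dentapen p of 0.010 is not by itself evidence of a device difference. The comparison that would be evidence has mean 1.25 and a p-value from about 0.19 to 0.02, depending on a correlation that the document does not report.

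Two stronger conclusions are not supported. The documents do not show that the heart-rate finding is a product of multiplicity, since it survives Bonferroni over four. Nor can it be concluded that pain, taken as the sole primary outcome, shows no device difference: the 0.105 is a Mann-Whitney p-value, and the planned paired analysis is not reported.

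**What to change.** 1. Limit the rule that a significant p-value indicates a difference between the techniques to tests that compare the devices within patients.
2. Replace the separate before-after heart-rate tests with the within-patient difference between devices in heart-rate change, with its 95% CI, computed from the individual data so that no correlation has to be assumed.
3. Treat the paired pain comparison as the single deciding outcome at two-sided 0.05, using the planned Wilcoxon signed-rank test in place of the Mann-Whitney test in Table 4. State plainly that the choice is post hoc, because results are already in the document.
4. Report heart rate and preference as supportive.
5. Delete the sentence that equates 0.05 with a 5% likelihood that the differences arose by chance.

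The cost is revised wording and two re-analyses of data already held. The downside is that a heart-rate result alone can no longer be claimed as the trial's finding. The post hoc label also means that the pain result carries less weight than one named as primary in advance.

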Cover letter

Title: Comparison Between the Dentapen and Vibraject: a Randomized Clinical Study on the Administration of Local Anaesthesia in Adult Patients.

Date: January 14, 2025

STUDY PROTOCOL

Ethical Approval

The study was conducted in compliance with the Helsinki Declaration. Each participant in this study was given a thorough explanation of the procedures and signed a consent form attesting to their comprehension. Ethical approval was obtained from the research centre at Riyadh Elm University prior to conducting this research (FPGRP/2023/715/906/892). The informed consent was obtained from the participants who volunteered in this research.

Outcome Measurement

In this study, each patient received two injections in both sides of the maxilla buccally next to the first molar, with the type of injection being randomly assigned. Immediately following each local anaesthesia injection, patients were requested to rate their pain intensity using the Visual Analogue Scale. Additionally, heart rate measurements were taken before and after each injection to monitor physiological responses to pain.

After both injections were completed, patients were asked to indicate their preferred injection. This preference was based on their subjective experience and was recorded by selecting the injection number (either the first or second) in the order they were administered for each patient. This method aimed to provide insights into patient comfort and pain perception associated

Inclusion Criteria:

- Individuals classified under American Society of Anesthesiologists classes I and II, indicating a healthy or mild systemic disease status.
- Individuals aged from 18 up to 65 years, encompassing both male and female patients.

- Individuals who required local anesthetic injections bilaterally in the buccal side of the upper posterior teeth. These injections were necessary for various dental procedures, including restorative, endodontic, or prosthodontic treatments, and volunteers as well were to be administered across both sides of upper posterior teeth.
- Individuals must be in good health, not currently taking any medication, and have no contraindications to the use of local anesthesia.
- Individuals who have the ability to understand both oral and written instructions, ensuring effective communication and comprehension throughout the study.

Exclusion Criteria:

- Individuals with allergies to local anesthetics, this is to prevent adverse reactions.

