The patient then returned after one hour, and the patient's heart rate being recorded before the administration of local anaesthesia. For this second injection, the alternative injection method was used on the other side, ensuring that each patient experienced both types of injections. Following the second injection, the patient's heart rate was measured once more to capture the immediate physiological response and the patient will be asked again to evaluate pain intensity with Visual Analogue Scale.

[figure not shown]

Figure 1: Flow chart of the study

This study design is a split mouth clinical trial which allowed for a within-subjects comparison, where each patient's reaction to both injection methods could be directly compared. The heart rate measurements before and after each injection provided objective data on the physiological response to the injections.

Steps of the Experiment

The experimental protocol was meticulously structured to evaluate the efficacy and patient response to two different local anaesthetic delivery systems. The steps were as follows:

Step I: Before administering a local anaesthetic, the patient's heart rate was checked with a pulse oximeter (Beurer Finger Pulse Oximeter). The results were recorded.

Step II: Patients were randomly assigned to get the injection of local anaesthetic at their initial appointment either with the Dentapen system (ramp-up) or with Vibraject. To simplify the protocol, a 27-gauge needle was used for all dental injections with bevel side directly headed to the injected site.

Step III: In the next appointment, after one hour on a digital timer, the other technique was used for the same patients on the other side. Hence, each patient was given local anaesthesia twice, once with the Dentapen system (ramp-up mode) and once with Vibraject.

Step IV: Immediately after each local anaesthesia injection operation, the patient was asked to use the Visual Analogue Scale to score the intensity of reported pain.

Step V: After administering a local anaesthetic, the patient's heart rate was measured with a pulse oximeter (Beurer Finger Pulse Oximeter). The results were recorded.

Step VI: After both injections were administered to each patient, they were asked which injection they would prefer by selecting the injection number (first or second) according to their order for each patient.

Risk of Bias

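### Heart rate is measured around both injections in every patient, but the two devices are never compared on it: one device's p=0.010 stands beside the other's p=0.712 without a test of their difference

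*Combined protocol and SAP*

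**What the plan says.** Under Outcome Measurement, "heart rate measurements were taken before and after each injection to monitor physiological responses to pain". Study Design adds a fresh baseline at the second visit, one hour later, with "the patient's heart rate being recorded before the administration of local anaesthesia". Each patient therefore supplies four readings: before and after, with each device.

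Study Design also states: "This study design is a split mouth clinical trial which allowed for a within-subjects comparison". The same sentence goes on to say that a patient's reactions to the two methods can be compared directly, and the next sentence presents heart rate as the objective measure of that reaction.

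The Statistical Analysis section is narrower. "The paired T-test was chosen for the heart rate data as it is designed to compare the means of two related groups", the example being "such as the same patients' heart rates before and after each injection", and the stated aim is "assessing whether there is a statistically significant change in heart rate following the administration of local anaesthesia". A test between techniques is described only for pain, where of the Wilcoxon test it says that "it was employed to evaluate the differences in pain scores between the two different injection techniques on the same patients". Table 3 follows this plan: a before-after paired t-test for Dentapen, one for Vibraject, and one for all 80 sites together.

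**The concern.** The heart-rate question that the design was built to answer is whether the response differs between devices. The planned tests answer another one: whether heart rate changes after each injection, one device at a time. Table 3 then shows one significant and one non-significant result side by side. The two changes can lie on opposite sides of 0.05 while the evidence that they differ is weak.

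The closing paragraph of Statistical Analysis adds to the risk, because it reads any p-value at or below 0.05 as pointing to a real difference between the techniques. Applied to the Dentapen row of Table 3, that reading is wrong: the row contains no comparison with Vibraject. At stake is whether a reader concludes, without a test, that one device raises heart rate more than the other.

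**Working it through.** **Inputs (Tables 2 and 3, n=40 per device)**

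| | Mean before | Mean after | SD before | SD after | SD of change |
|---|---|---|---|---|---|
| Dentapen | 70.225 | 71.750 | 10.04984 | 9.94794 | 3.56613 |
| Vibraject | 70.775 | 71.050 | 10.40091 | 9.35058 | 4.67940 |

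**1. Reproduce Table 3.** t = mean change / (SD of change / √n), with the table's sign (before minus after).
- Dentapen: −1.525 / (3.56613/√40) = −1.525/0.56386 = −2.705; p=0.010.
- Vibraject: −0.275 / (4.67940/√40) = −0.275/0.73988 = −0.372; p=0.712.

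Both agree with the table.

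**2. The contrast that is missing.** Difference in mean change (after minus before) = 1.525 − 0.275 = 1.25 bpm, higher for Dentapen. With ρ the within-patient correlation of the two changes,

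SE² = (3.56613² + 4.67940² − 2ρ × 3.56613 × 4.67940)/40 = (34.614 − 33.375ρ)/40.

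| ρ (assumed) | SE | p (39 df) | 95% CI |
|---|---|---|---|
| −0.2 | 1.02 | 0.23 | −0.81 to 3.31 |
| 0 | 0.93 | 0.19 | −0.63 to 3.13 |
| 0.5 | 0.67 | 0.07 | −0.10 to 2.60 |
| 0.7 | 0.53 | 0.02 | 0.18 to 2.32 |

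The result reaches 0.05 when SE = 1.25/2.0227 = 0.618, that is at ρ = (34.614 − 40 × 0.618²)/33.375, about 0.58.

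**3. Can ρ be recovered from the Overall row?** No. Its SD follows from the two per-device rows alone: √[(39 × 12.717 + 39 × 21.897 + 80 × 0.625²)/79] = 4.181, the value in Table 3. It carries no information on pairing.

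**4. What baseline adjustment adds, treating the devices as independent.** Results say: "The mean heart rate before treatment is slightly lower for Dentapen", a gap of 0.55 bpm. Covariance of before and after = (SDb² + SDa² − SDchange²)/2: 93.62 for Dentapen and 86.86 for Vibraject.
- Pooled slope = (93.62 + 86.86)/(101.00 + 108.18) = 0.863.
- Adjusted contrast = (71.75 − 71.05) + 0.863 × 0.55 = 1.17 bpm.
- Residual variance = 39 × (98.96 + 87.43 − 0.863 × 180.48)/77 = 15.54, so SE = √(15.54 × 2/40) = 0.88; p about 0.19.
- Variance against the change score: 0.882²/0.930² = 0.90, about 10% lower.

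**5. The same question within patients, under a simple model.** Let each reading be a patient effect plus a visit effect plus independent reading noise, with k the ratio of visit to noise variance. The within-patient slope is k/(k+1), and the variance of the adjusted contrast relative to the change-score contrast is (2k+1)/(2(k+1)).
- k=0 gives 0.50; k=1 gives 0.75; k=5 gives 0.92.
- The tables bound k from above. Noise variance = 34.614/4 = 8.65. The average variance of a reading is (104.59 + 93.20)/2 = 98.9. With no patient effect at all, k = (98.9 − 8.65)/8.65, about 10.4, and the ratio is 0.96.

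The reduction therefore lies between about 4% and 50%, and the adjusted contrast between 0.70 bpm (slope 0) and 0.70 + 0.91 × 0.55 = 1.20 bpm. This model implies ρ=0, so these reductions apply to the SE of 0.93 and not to 0.67. Its 4% floor is below the 10% of step 4 because the model makes before and after variances equal, whereas Table 2 shows a larger spread before than after with Vibraject.

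**The case against.** The strongest objection is that the heart-rate plan is consistent with its own stated aim. It sets out to detect a change after anaesthesia, tests that, and the text under Table 3 describes each device's result without declaring that the devices differ. That stands as a description: the documents contain no explicit false device claim on heart rate. It does not answer the gap between the purpose given under Study Design and the tests chosen.

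A reader might also infer that the plan has a heart-rate device comparison which loses precision by using change scores. The documents do not support this, since there is no such comparison to lose precision. Nor do the per-device figures show it. Regressing after on before gives a residual variance of 0.96 (Dentapen) and 0.81 (Vibraject) times the change-score variance, but each Table 3 test estimates a single mean change with no comparator, and adjusting for the patient's own baseline does not improve that estimate.

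It would be equally wrong to say that the 0.55 bpm baseline gap goes uncorrected by change scores. Subtraction already removes it with a slope of 1; a slope of 0.863 moves the contrast by only 1.25 − 1.17 = 0.08 bpm.

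Finally, estimating the slope from 40 patients costs about 3% in variance, so at the 4% end of the range the net gain is close to nil. That stands, and it is why adjustment is a refinement and not the main point.

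**Conclusion.** The point holds as an omission: heart rate is never compared between devices, although the design and the data allow it, and the two separate p-values cannot stand in for that comparison. The estimated difference in change is 1.25 bpm, with p about 0.19 if the two changes are uncorrelated and about 0.07 if their correlation is 0.5. That correlation is an assumption. Only above about 0.58 would the unadjusted contrast reach 0.05, so the documents support neither a claim that the devices differ nor a claim that they do not.

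The gain from baseline adjustment is real in principle but cannot be fixed from the documents. It is about 10% of variance with devices treated as independent, and anywhere from about 4% to 50% under the simple model. No reversal of a reported result follows from it. This is a worthwhile addition, not a flaw that invalidates the reported before-after tests, whose arithmetic reproduces.

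**What to change.** Add one within-patient device comparison of post-injection heart rate. A suitable form is a linear mixed model with device, period, the pre-injection heart rate for that injection, the patient's mean pre-injection heart rate, and a patient random effect. The patient mean separates the within-patient slope, which matters for the device contrast, from the between-patient slope. A simpler alternative is to regress the within-patient difference in after values on the difference in before values, with a sequence (period) term; without that term the regression leaves out period.

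Report the adjusted device difference with its 95% CI, and give the correlation between the two changes so that readers can check the precision. Label the analysis post hoc, because results are already reported. State beside Table 3 that its separate p-values do not test a difference between devices.

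All four readings per patient already exist. The cost is one model and one or two of 39 degrees of freedom; the post hoc status cannot be undone.

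### Heart rate is tested only before versus after injection; no test compares Dentapen with Vibraject, so a device difference is neither shown nor excluded

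*Combined protocol and SAP*

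**What the plan says.** The Statistical Analysis section introduces the tests thus: "The primary statistical tests employed were the paired T-test for analysing the heart rate data", alongside a Wilcoxon test for pain. It gives before versus after each injection as the use of the heart-rate test and calls the test "particularly suitable for assessing whether there is a statistically significant change in heart rate following the administration of local anaesthesia". The pain test, by contrast, is "employed to evaluate the differences in pain scores between the two different injection techniques on the same patients". No between-technique test is named for heart rate.

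The section sets the threshold ("A p-value of 0.05 or less was considered statistically significant") and then gives one general reading of a result that meets it: "suggesting a real difference between the two techniques that is not due to random variation".

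The Study Design section says the split-mouth layout means each patient's "reaction to both injection methods could be directly compared". Step II of Steps of the Experiment randomises which device is used first: "Patients were randomly assigned to get the injection of local anaesthetic at their initial appointment".

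All three rows of Table 3 (overall, Dentapen, Vibraject) are before minus after. The text reports a significant rise for Dentapen and adds that "no significant differences were observed in the mean heart rate measurements between the overall and Vibraject before and after injection". The text above Table 2 sets the two devices' means side by side without a test or an interval.

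**The concern.** The question of the trial is Dentapen against Vibraject. For heart rate, the plan answers a different one: did heart rate change after an injection? The paired t-test is sound for that within each device, but it contains no comparison of the devices.

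The layout of Table 3 invites a false step. One row is starred, the other is not, and the only rule given for reading p-values speaks of a difference between techniques. A reader who applies that rule to the Dentapen p=0.010 would conclude that Dentapen raises heart rate more than Vibraject. That was never tested. Two within-device tests can fall on opposite sides of 0.05 when the devices have the same true effect, as the check below shows.

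**Working it through.** **Inputs (Table 3, signs reversed so that a rise is positive).** Dentapen: mean 1.525 bpm, SD 3.56613, n=40. Vibraject: mean 0.275, SD 4.67940, n=40. Overall: mean 0.900, SD 4.18133, n=80.

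**Reproducing Table 3.** With t = mean/(SD/√n) on n−1 df:

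- Dentapen: 1.525/0.5639 = 2.705, p=0.0101.
- Vibraject: 0.275/0.7399 = 0.372, p=0.712.
- Overall: 0.900/0.4675 = 1.925 on 79 df, p=0.058.

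All three rows match the table, so they are before/after tests and none is a device contrast.

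**The missing contrast.** The difference between the two changes is 1.525 − 0.275 = 1.25 bpm. Its SD within patients is √(3.566² + 4.679² − 2r × 3.566 × 4.679), where r is the correlation between a patient's two changes. The SE is this SD/√40, with 39 df (t critical value 2.023).

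The documents do not report r. The overall row cannot supply it, because its SD follows from the two device rows alone: √[(39×3.566² + 39×4.679² + 40×(0.625² + 0.625²))/79] = 4.181. So r is varied here as an assumption:

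| r | SD | SE | 95% CI (bpm) | p |
|---|---|---|---|---|
| −0.3 | 6.68 | 1.056 | −0.89 to 3.39 | 0.24 |
| 0 | 5.88 | 0.930 | −0.63 to 3.13 | 0.19 |
| 0.5 | 4.23 | 0.669 | −0.10 to 2.60 | 0.069 |
| 0.6 | 3.82 | 0.604 | 0.03 to 2.47 | 0.045 |

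Setting p=0.05 and solving gives r = 0.579.

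**How often the two rows disagree when the devices do not differ.** Assume the same true rise with both devices and the Table 3 SDs. At a rise of 0.9 bpm (the pooled mean), the noncentral t gives power 0.344 for Dentapen and 0.220 for Vibraject. At r=0, exactly one row is significant with probability 0.344×0.780 + 0.220×0.656 = 0.41. Simulation gives about 30% at r=0.5.

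| Common true rise | Exactly one significant, r=0 | r=0.5 |
|---|---|---|
| 0 bpm | 9.5% | 8% |
| 0.5 bpm | 21% | 16% |
| 0.9 bpm | 41% | about 30% |
| 3 bpm | 2% | 2% |

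**Injection order.** If k of the 40 patients had Dentapen first, the unadjusted contrast carries |40−2k|/40 of any difference between first and second injections. At 24:16 that is 8/40 = 0.2 of it. The split and the randomisation method are not stated. Under simple 1:1 randomisation (an assumption), a split of 24:16 or worse has probability 27%.

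**The case against.** The strongest reply is that the documents never say the devices differ on heart rate. The results text reports only a rise after Dentapen, which is what that row tests, and the row labels are plain. The sentence about techniques directly follows the paragraph on the pain test, where it fits. The Outcome Measurement section says heart rate was taken to monitor the response to pain, which a before/after test serves. The before/after use is also introduced as an example, so another paired contrast is not ruled out. Finally, the word primary may mean only the main tests used, since no primary outcome is named.

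These points are fair, and they limit the issue to a missing analysis and a risk of misreading. They do not supply the comparison: no heart-rate contrast between devices is specified or reported.

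Three smaller points stand in part:

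- Large differences do look unlikely: the upper 95% limit is at most 3.39 bpm for the values of r tabulated.
- The 41% counts either device as the lone significant one. The pattern actually seen, Dentapen only, has probability 0.344×0.780 = 27% at r=0. All these rates depend on the assumed common rise and illustrate the problem; they are not evidence of an error here.
- The overall row treats 80 changes from 40 patients as independent. Calling the before/after test valid therefore applies to the two device rows only. Based on 40 patient means, the overall p would be 0.027 at r=−0.3, 0.060 at r=0 and 0.12 at r=0.5.

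**Conclusion.** The concern holds. Neither the plan nor Table 3 contains a Dentapen-versus-Vibraject test of heart rate, although the design was chosen to allow one. The estimated difference is 1.25 bpm more rise with Dentapen. Whether it meets the 0.05 threshold turns on a correlation the documents do not give: it does not below r of about 0.58 and does above it. Only the patient-level data can decide.

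This rests on the Table 3 means and SDs, complete pairs in all 40 patients, and no adjustment for order. It should be fixed. Nothing in the two device rows is miscalculated, but the trial's own comparison is unanswered for this outcome.

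**What to change.** 1. For the device comparison on heart rate, use a paired t-test of (after − before) with Dentapen minus (after − before) with Vibraject, n=40. Report the mean difference and its 95% CI. State that the contrast was added after the before/after results were known.
2. Check it with a model that adjusts for injection order, and report how many patients received each order.
3. Keep the before/after rows of Table 3 as description. If the overall row stays, base it on one mean change per patient.
4. Limit the Statistical Analysis wording about a difference between techniques to between-device contrasts.

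The cost is one paired contrast, one order-adjusted check on data already collected, and a reworded sentence. The price for the authors is that the only significant heart-rate result, Dentapen p=0.010, becomes descriptive.
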